Follow-up is conducted to obtain general information on the pregnancy; in addition, follow-up is conducted to obtain information on EDP outcome for all EDP reports with pregnancy outcome unknown. A pregnancy is followed until completion or until pregnancy termination (e.g., induced abortion) and Pfizer is notified of the outcome. This information is provided as a follow-up to the initial EDP report. In the case of a live birth, the structural integrity of the neonate can be assessed at the time of birth. In the event of a termination, the reason(s) for termination should be specified and, if clinically possible, the structural integrity of the terminated fetus should be assessed by gross visual inspection (unless pre-procedure test findings are conclusive for a congenital anomaly and the findings are reported).

If the outcome of the pregnancy meets the criteria for an SAE (e.g., ectopic pregnancy, spontaneous abortion, intrauterine fetal demise, neonatal death, or congenital anomaly [in a live born, a terminated fetus, an intrauterine fetal demise, or a neonatal death]), the procedures for reporting SAEs should be followed.

PFIZER CONFIDENTIAL

CT24-WI-GL02-RF01 6.0 Non-Interventional Study Protocol Template For Primary Data Collection Study 01-

Aug-2023

Page 44 of 57

**CLINICAL AND MEDICAL CONTROLLED DOCUMENT (CMCD)
REQUIRED FORM/TEMPLATE**

Identifier	Version	Title	Effective Date
CT24-WI-GL02-RF01	6.0	NON-INTERVENTIONAL STUDY PROTOCOL TEMPLATE FOR PRIMARY DATA COLLECTION STUDY	01-Aug-2023

Additional information about pregnancy outcomes that are reported as SAEs follows:

- Spontaneous abortion includes miscarriage and misses abortion;
- Neonatal deaths that occur within 1 month of birth should be reported, without regard to causality, as SAEs. In addition, infant deaths after 1 month should be reported as SAEs when the investigator assesses the infant death as related or possibly related to exposure to investigational product.

Additional information regarding the exposure during pregnancy may be requested. Further follow-up of birth outcomes will be handled on a case-by-case basis (e.g., follow-up on preterm infants to identify developmental delays).

In the case of paternal exposure, the study participant will be provided with the Pregnant Partner Release of Information Form to deliver to his partner. It must be documented that the study participant was given this letter to provide to his partner.

Exposure during breastfeeding

Scenarios of exposure during breastfeeding must be reported, irrespective of the presence of an associated AE. An exposure during breastfeeding report is not created when a Pfizer drug specifically approved for use in breastfeeding women (e.g., vitamins) is administered in accord with authorized use. However, if the infant experiences an AE associated with such a drug's administration, the AE is reported together with the exposure during breastfeeding.

Medication error

A medication error is any unintentional error in the prescribing, dispensing, or administration of a medicinal product that may cause or lead to inappropriate medication use or patient harm while in the control of the health care professional, patient, or consumer. Such events may be related to professional practice, health care products, procedures, and systems including prescribing; order communication; product labeling, packaging, and nomenclature; compounding; dispensing; distribution; administration; education; monitoring; and use.

Medication errors include:

- Near misses, involving or not involving a patient directly (e.g., inadvertent/erroneous administration, which is the accidental use of a product outside of labeling or prescription on the part of the healthcare provider or the patient/consumer);
- Confusion with regard to invented name (e.g., trade name, brand name).

The investigator must submit the following medication errors to Pfizer, irrespective of the presence of an associated AE/SAE:

- Medication errors involving patient exposure to the product, whether or not the medication error is accompanied by an AE.

PFIZER CONFIDENTIAL

CT24-WI-GL02-RF01 6.0 Non-Interventional Study Protocol Template For Primary Data Collection Study 01-

Aug-2023

Page 45 of 57

**CLINICAL AND MEDICAL CONTROLLED DOCUMENT (CMCD)
REQUIRED FORM/TEMPLATE**

Identifier	Version	Title	Effective Date
CT24-WI-GL02-RF01	6.0	NON-INTERVENTIONAL STUDY PROTOCOL TEMPLATE FOR PRIMARY DATA COLLECTION STUDY	01-Aug-2023

- Medication errors that do not involve a patient directly (e.g., potential medication errors or near misses). When a medication error does not involve patient exposure to the product the following minimum criteria constitute a medication error report:
 - An identifiable reporter;
 - A suspect product;
 - The event medication error.

Overdose, Misuse, Extravasation

Reports of overdose, misuse, and extravasation associated with the use of a Pfizer product are reported to Pfizer by the investigator, irrespective of the presence of an associated AE/SAE.

Lack of Efficacy

Reports of lack of efficacy to a Pfizer product are reported to Pfizer by the investigator, irrespective of the presence of an associated AE/SAE or the indication for use of the Pfizer product.

Occupational Exposure

Reports of occupational exposure to a Pfizer product are reported to Pfizer by the investigator, irrespective of the presence of an associated AE/SAE.

11.1. Single reference safety document

The prescribing information will serve as the single reference safety document during the course of the study, which will be used by Pfizer safety to assess any safety events reported to Pfizer Safety by the investigator during the course of this study.

The single reference safety document should be used by the investigator for prescribing purposes and guidance.

12. PLANS FOR DISSEMINATING AND COMMUNICATING STUDY RESULTS

The results of the study will be published in international or national congress and index journal.

In the event of any prohibition or restriction imposed (e.g., clinical hold) by an applicable competent authority in any area of the world, or if the investigator is aware of any new information which might influence the evaluation of the benefits and risks of a Pfizer product, Pfizer should be informed immediately.

In addition, the investigator will inform Pfizer immediately of any urgent safety measures taken by the investigator to protect the study patients against any immediate hazard, and of any serious breaches of this NI study protocol that the investigator becomes aware of.

PFIZER CONFIDENTIAL

CT24-WI-GL02-RF01 6.0 Non-Interventional Study Protocol Template For Primary Data Collection Study 01-

Aug-2023

Page 46 of 57

**CLINICAL AND MEDICAL CONTROLLED DOCUMENT (CMCD)
REQUIRED FORM/TEMPLATE**

Identifier	Version	Title	Effective Date
CT24-WI-GL02-RF01	6.0	NON-INTERVENTIONAL STUDY PROTOCOL TEMPLATE FOR PRIMARY DATA COLLECTION STUDY	01-Aug-2023

Identifier	Version	Title	Effective Date
CT24-WI-GL02-RF01	6.0	NON-INTERVENTIONAL STUDY PROTOCOL TEMPLATE FOR PRIMARY DATA COLLECTION STUDY	01-Aug-2023

15. LIST OF FIGURES

None.

ANNEX 1. LIST OF STAND ALONE DOCUMENTS

None.

ANNEX 2. ENCePP CHECKLIST FOR STUDY PROTOCOLS

ENCePP Checklist for Study Protocols (Revision 4)

Adopted by the ENCePP Steering Group on 15/10/2018

The [European Network of Centres for Pharmacoepidemiology and Pharmacovigilance \(ENCePP\)](#) welcomes innovative designs and new methods of research. This Checklist has been developed by ENCePP to stimulate consideration of important principles when designing and writing a pharmacoepidemiological or pharmacovigilance study protocol. The Checklist is intended to promote the quality of such studies, not their uniformity. The user is also referred to the [ENCePP Guide on Methodological Standards in Pharmacoepidemiology](#), which reviews and gives direct electronic access to guidance for research in pharmacoepidemiology and pharmacovigilance.

For each question of the Checklist, the investigator should indicate whether or not it has been addressed in the study protocol. If the answer is "Yes", the section number of the protocol where this issue has been discussed should be specified. It is possible that some questions do not apply to a particular study (for example, in the case of an innovative study design). In this case, the answer 'N/A' (Not Applicable) can be checked and the "Comments" field included for each section should be used to explain why. The "Comments" field can also be used to elaborate on a "No" answer.

This Checklist should be included as an Annex by marketing authorisation holders when submitting the protocol of a non-interventional post-authorisation safety study (PASS) to a regulatory authority (see the [Guidance on the format and content of the protocol of non-interventional post-authorisation safety studies](#)). The Checklist is a supporting document and does not replace the format of the protocol for PASS presented in the Guidance and Module VIII of the Good pharmacovigilance practices (GVP).

Study title: Impact of tafamidis in Colombian patients diagnosed with ATTR-CM on quality of life during two year of follow-up

EU PAS Register® number: EUPAS105913
Study reference number (if applicable): NA

Section 1: Milestones	Yes	No	N/A	Section Number
1.1 Does the protocol specify timelines for				

PFIZER CONFIDENTIAL

CT24-WI-GL02-RF01 6.0 Non-Interventional Study Protocol Template For Primary Data Collection Study 01-

Aug-2023

Page 50 of 57

**CLINICAL AND MEDICAL CONTROLLED DOCUMENT (CMCD)
REQUIRED FORM/TEMPLATE**

Identifier	Version	Title	Effective Date
CT24-WI-GL02-RF01	6.0	NON-INTERVENTIONAL STUDY PROTOCOL TEMPLATE FOR PRIMARY DATA COLLECTION STUDY	01-Aug-2023

Section 1: Milestones	Yes	No	N/A	Section Number
1.1.1 Start of data collection ¹				6
1.1.2 End of data collection ²				6
1.1.3 Progress report(s)				6
1.1.4 Interim report(s)				6
1.1.5 Registration in the EU PAS Register®				6
1.1.6 Final report of study results.				6

Comments:

Section 2: Research question	Yes	No	N/A	Section Number
2.1 Does the formulation of the research question and objectives clearly explain:				8
2.1.1 Why the study is conducted? (e.g. to address an important public health concern, a risk identified in the risk management plan, an emerging safety issue)				7
2.1.2 The objective(s) of the study?				8
2.1.3 The target population? (i.e., population or subgroup to whom the study results are intended to be generalized)				9.2.1
2.1.4 Which hypothesis(-es) is (are) to be tested?				8
2.1.5 If applicable, that there is no a priori hypothesis?				

Comments:

Section 3: Study design	Yes	No	N/A	Section Number
3.1 Is the study design described? (e.g., cohort, case-control, cross-sectional, other design)				9.1

¹ Date from which information on the first study is first recorded in the study dataset or, in the case of secondary use of data, the date from which data extraction starts.

² Date from which the analytical dataset is completely available.

**CLINICAL AND MEDICAL CONTROLLED DOCUMENT (CMCD)
REQUIRED FORM/TEMPLATE**

Identifier	Version	Title	Effective Date
CT24-WI-GL02-RF01	6.0	NON-INTERVENTIONAL STUDY PROTOCOL TEMPLATE FOR PRIMARY DATA COLLECTION STUDY	01-Aug-2023

Section 3: Study design	Yes	No	N/ A	Section Number
3.2 Does the protocol specify whether the study is based on primary, secondary, or combined data collection?				9.1
3.3 Does the protocol specify measures of occurrence? (e.g., rate, risk, prevalence)				
3.4 Does the protocol specify measure(s) of association? (e.g., risk, odds ratio, excess risk, rate ratio, hazard ratio, risk/rate difference, number needed to harm (NNH))				9.7.5.2
3.5 Does the protocol describe the approach for the collection and reporting of adverse events/adverse reactions? (e.g., adverse events that will not be collected in case of primary data collection)				10

Comments:

Section 4: Source and study populations	Yes	No	N/ A	Section Number
4.1 Is the source population described?				9
4.2 Is the planned study population defined in terms of:				
4.2.1 Study time period				9.2
4.2.2 Age and sex				9.2
4.2.3 Country of origin				9.2
4.2.4 Disease/indication				9.2
4.2.5 Duration of follow-up				9.2
4.3 Does the protocol define how the study population will be sampled from the source population? (e.g., event or inclusion/exclusion criteria)				9.2

Comments:

PFIZER CONFIDENTIAL

CT24-WI-GL02-RF01 6.0 Non-Interventional Study Protocol Template For Primary Data Collection Study 01-

Aug-2023

Page 52 of 57

**CLINICAL AND MEDICAL CONTROLLED DOCUMENT (CMCD)
REQUIRED FORM/TEMPLATE**

Identifier	Version	Title	Effective Date
CT24-WI-GL02-RF01	6.0	NON-INTERVENTIONAL STUDY PROTOCOL TEMPLATE FOR PRIMARY DATA COLLECTION STUDY	01-Aug-2023

Section 5: Exposure definition and measurement	Yes	No	N/A	Section Number
5.1 Does the protocol describe how the study exposure is defined and measured? (e.g., operational details for defining and categorising exposure, measurement of dose and duration of drug exposure)				9.3
5.2 Does the protocol address the validity of the exposure measurement? (e.g., precision, accuracy, use of validation sub-study)				9.1
5.3 Is exposure categorised according to time windows?				9.3
5.4 Is intensity of exposure addressed? (e.g., dose, duration)				9.3
5.5 Is exposure categorised based on biological mechanism of action and taking into account the pharmacokinetics and pharmacodynamics of the drug?				
5.6 Is (are) (an) appropriate comparator(s) identified?				9.3

Comments:

Section 6: Outcome definition and measurement	Yes	No	N/A	Section Number
6.1 Does the protocol specify the primary and secondary (if applicable) outcome(s) to be investigated?				9.3
6.2 Does the protocol describe how the outcomes are defined and measured?				9.3
6.3 Does the protocol address the validity of outcome measurement? (e.g., precision, accuracy, sensitivity, specificity, positive predictive value, use of validation sub-study)				9.3
6.4 Does the protocol describe specific outcomes relevant for Health Technology Assessment? (e.g. HRQoL, QALYs, DALYs, health care services utilisation, burden of disease or treatment, compliance, disease management)				

Comments:

**CLINICAL AND MEDICAL CONTROLLED DOCUMENT (CMCD)
REQUIRED FORM/TEMPLATE**

Identifier	Version	Title	Effective Date
CT24-WI-GL02-RF01	6.0	NON-INTERVENTIONAL STUDY PROTOCOL TEMPLATE FOR PRIMARY DATA COLLECTION STUDY	01-Aug-2023

Section 7: Bias	Yes	No	N/A	Section Number
7.1 Does the protocol address ways to measure confounding? (e.g. confounding by indication)				9.3
7.2 Does the protocol address selection bias? (e.g. healthy user/adherer bias)				
7.3 Does the protocol address information bias? (e.g. misclassification of exposure and outcomes, time-related bias)				9.3

Comments:

Section 8: Effect measure modification	Yes	No	N/A	Section Number
8.1 Does the protocol address effect modifiers? (e.g. collection of data on known effect modifiers, subgroup analyses, anticipated direction of effect)				9.3

Comments:

Section 9: Data sources	Yes	No	N/A	Section Number
9.1 Does the protocol describe the data source(s) used in the study for the ascertainment of:				
9.1.1 Exposure? (e.g. pharmacy dispensing, general practice prescribing, claims data, self-report, face-to-face interview)				9.4
9.1.2 Outcomes? (e.g. clinical records, laboratory markers or values, claims data, self-report, patient interview including scales and questionnaires, vital statistics)				9.4
9.1.3 Covariates and other characteristics?				9.4
9.2 Does the protocol describe the information available from the data source(s) on:				
9.2.1 Exposure? (e.g. date of dispensing, drug quantity, dose, number of days of supply prescription, daily dosage, prescriber)				9.3
9.2.2 Outcomes? (e.g. date of occurrence, multiple event, severity measures related to event)				9.3
9.2.3 Covariates and other characteristics? (e.g. age, sex, clinical and drug use history, co-morbidity, co-medications, lifestyle)				9.3

PFIZER CONFIDENTIAL

CT24-WI-GL02-RF01 6.0 Non-Interventional Study Protocol Template For Primary Data Collection Study 01-

Aug-2023

Page 54 of 57

**CLINICAL AND MEDICAL CONTROLLED DOCUMENT (CMCD)
REQUIRED FORM/TEMPLATE**

Identifier	Version	Title	Effective Date
CT24-WI-GL02-RF01	6.0	NON-INTERVENTIONAL STUDY PROTOCOL TEMPLATE FOR PRIMARY DATA COLLECTION STUDY	01-Aug-2023

Section 9: Data sources	Yes	No	N/ A	Section Number
9.3 Is a coding system described for:				
9.3.1 Exposure? (e.g. WHO Drug Dictionary, Anatomical Therapeutic Chemical (ATC) Classification System)				9.1
9.3.2 Outcomes? (e.g. International Classification of Diseases (ICD), Medical Dictionary for Regulatory Activities (MedDRA))				
9.3.3 Covariates and other characteristics?				9.3
9.4 Is a linkage method between data sources described? (e.g. based on a unique identifier or other)				9.4

Comments:

Section 10: Analysis plan	Yes	No	N/ A	Section Number
10.1 Are the statistical methods and the reason for their choice described?				9.7
10.2 Is study size and/or statistical precision estimated?				9.5
10.3 Are descriptive analyses included?				9.7
10.4 Are stratified analyses included?				9.7
10.5 Does the plan describe methods for analytic control of confounding?				9.7
10.6 Does the plan describe methods for analytic control of outcome misclassification?				
10.7 Does the plan describe methods for handling missing data?				9.7
10.8 Are relevant sensitivity analyses described?				9.7

Comments:

Section 11: Data management and quality control	Yes	No	N/ A	Section Number
11.1 Does the protocol provide information on data storage? (e.g. software and IT environment, database maintenance and anti-fraud protection, archiving)				9.6
11.2 Are methods of quality assurance described?				9.8

PFIZER CONFIDENTIAL

CT24-WI-GL02-RF01 6.0 Non-Interventional Study Protocol Template For Primary Data Collection Study 01-

Aug-2023

Page 55 of 57

**CLINICAL AND MEDICAL CONTROLLED DOCUMENT (CMCD)
REQUIRED FORM/TEMPLATE**

Identifier	Version	Title	Effective Date
CT24-WI-GL02-RF01	6.0	NON-INTERVENTIONAL STUDY PROTOCOL TEMPLATE FOR PRIMARY DATA COLLECTION STUDY	01-Aug-2023

Section 11: Data management and quality control	Yes	No	N/A	Section Number
11.3 Is there a system in place for independent review of study results?				

Comments:

Section 12: Limitations	Yes	No	N/A	Section Number
12.1 Does the protocol discuss the impact on the study results of: 12.1.1 Selection bias? 12.1.2 Information bias? 12.1.3 Residual/unmeasured confounding? (e.g. anticipated direction and magnitude of such biases, validation sub-study, use of validation and external data, analytical methods).	  	  	  	9.9 9.9 9.9
12.2 Does the protocol discuss study feasibility? (e.g. study size, anticipated exposure uptake, duration of follow-up in a cohort study, patient recruitment, precision of the estimates)				9.1;9.5

Comments:

Section 13: Ethical/data protection issues	Yes	No	N/A	Section Number
13.1 Have requirements of Ethics Committee/ Institutional Review Board been described?				10
13.2 Has any outcome of an ethical review procedure been addressed?				10
13.3 Have data protection requirements been described?				10

Comments:

Section 14: Amendments and deviations	Yes	No	N/A	Section Number
14.1 Does the protocol include a section to document amendments and deviations?				

PFIZER CONFIDENTIAL

CT24-WI-GL02-RF01 6.0 Non-Interventional Study Protocol Template For Primary Data Collection Study 01-

Aug-2023

Page 56 of 57

**CLINICAL AND MEDICAL CONTROLLED DOCUMENT (CMCD)
REQUIRED FORM/TEMPLATE**

Identifier	Version	Title	Effective Date
CT24-WI-GL02-RF01	6.0	NON-INTERVENTIONAL STUDY PROTOCOL TEMPLATE FOR PRIMARY DATA COLLECTION STUDY	01-Aug-2023

Comments:

Section 15: Plans for communication of study results	Yes	No	N/A	Section Number
15.1 Are plans described for communicating study results (e.g. to regulatory authorities)?				12
15.2 Are plans described for disseminating study results externally, including publication?				12

Comments:

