9.7.4. Handling of Missing Data

There will be no imputation or replacement of missing data. All analyses will be conducted on observed cases. All patients will be included in the descriptive analysis limited with the information recollect. The missing data will be included in the study report. Analysis with case complete will not be conducted.

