9.9. Limitations of the research methods

This study has the following limitations:

- The information of the patient in the baseline will be limited to data available in the clinical records and awareness of the patient.
- The complete information of hospitalizations will depend on the access to medical records provided by the patients.
- The number of patients recruited will likely be small which affects the subgroup analysis.
- The patients may have already started treatment prior to start of the study. This could make it difficult to adequately measure baseline QoL.
- Availability of 6 Minute walk test and scintigraphy for all patients during the follow-up due to the management of ATTR-CM patients have not been standardized.
- Although the official language of Colombia is Spanish, the languages and dialects of ethnic groups are also recognized as official. However, only around 5% of the population recognizes itself as belonging to an Indigenous or Rrom group (25).

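### Annex 2 claims sensitivity analyses and a discussion of selection and confounding that sections 9.7 and 9.9 do not contain, while the month-24 KCCQ summary covers only selected survivors

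*Protocol*

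**What the plan says.** **Annex 2 (ENCePP checklist).**
- Item 10.8, "Are relevant sensitivity analyses described", is ticked Yes with section 9.7 as the location.
- Item 12.1, "Does the protocol discuss the impact on the study results of: 12.1.1 Selection bias", is ticked Yes with section 9.9 as the location, as are its parts on information bias (12.1.2) and residual or unmeasured confounding (12.1.3).
- Item 7.2, "Does the protocol address selection bias", is marked N/A. The comment field beneath it is empty, although the checklist instructions ask for an explanation of an N/A.

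**Section 9.7.** Section 9.7.4 rules out imputation and complete-case analysis and states: "All analyses will be conducted on observed cases". Section 9.7.3.2 lists subgroups, among them supply delay and time on tafamidis before entry. Section 9.7.5.1 gives medians and IQRs for continuous variables. Section 9.7.5.2 adds paired tests and, as exploratory work if numbers permit, regression and repeated-measures mixed models.

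**Section 9.9.** It has six bullets: baseline data limited to records and patient awareness, hospitalisation data dependent on records the patient provides, small numbers ("The number of patients recruited will likely be small which affects the subgroup analysis"), treatment started before baseline KCCQ, uneven availability of 6MWT and scintigraphy, and language groups.

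**Sections 6, 9.1 and 9.2.** Patients treated from August 2022 to August 2023 are invited, and data collection starts on 15 November 2023. Follow-up stops at death, withdrawal, termination of treatment, loss, or month 24.

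**The concern.** The checklist tells its reader where in the protocol certain safeguards can be found, and on following the references they are not there. If that were all, it would be a clerical slip.

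It goes further because the content that is missing is content this design needs. The primary objective is the impact of tafamidis on KCCQ over two years, in a single cohort with no comparator. A patient contributes a month-24 score only after surviving from prescription to consent, then staying alive, on treatment and in contact. Each of these conditions is plausibly related to health status, and the observed-case rule gives no view of those who fail them. Section 9.2 nevertheless calls the cohort representative of patients in Colombia. At stake is whether a stable or rising KCCQ at month 24 can be told apart from the gradual loss of the sickest patients.

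**Working it through.** The protocol states no figure on this point, so there is nothing to reproduce. The check is a comparison of text followed by an illustration.

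**1. Checklist against the sections it cites**

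| Item | Entry | What the cited section holds |
|---|---|---|
| 10.8 sensitivity analyses | Yes, 9.7 | Summaries, subgroups, the observed-case rule, exploratory models. No sensitivity analysis named or described. |
| 12.1.1 selection bias | Yes, 9.9 | A language-group remark with no stated effect on results. Nothing on survivors or consenters. |
| 12.1.2 information bias | Yes, 9.9 | Covered in substance (records, late baseline). Not disputed. |
| 12.1.3 residual confounding | Yes, 9.9 | Not mentioned. |
| 7.2 selection bias addressed | N/A | Out of line with the Yes at 12.1.1. |

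**2. Selection before enrolment (illustration)**

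Inputs: treatment window from 9.2; start of data collection from section 6; mortality of 29.5% at 30 months on tafamidis in the pivotal trial, quoted in section 7. Assumptions: constant hazard, the trial's mortality applies here, and enrolment on the first possible day.

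Formula: probability of death by month t = 1 − 0.705^(t/30).

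- Earliest prescriptions, 15.5 months before collection starts: 1 − 0.705^(15.5/30) = 16.5%.
- Latest, 2.5 months before: 1 − 0.705^(2.5/30) = 2.9%.

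So roughly 3% to 16% could have died before they could consent.

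**3. Deaths by month 24 (same assumptions)**

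- From prescription: 1 − 0.705^(24/30) = 24.4%, or about 12 of 50.
- Among patients already enrolled the share is smaller. For the earliest, 24 − 15.5 = 8.5 months remain: 1 − 0.705^(8.5/30) = 9.4%. For the latest, 24 − 2.5 = 21.5 months remain: 1 − 0.705^(21.5/30) = 22.2%.

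Withdrawal, end of treatment and loss come on top. The protocol gives no rate for these.

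**4. Effect on an observed-case mean**

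Formula: shift = p × g, where p is the share without a score and g is how much worse their change is than in observed patients. Both are assumptions. The values of g are the three KCCQ thresholds in 9.3.1.

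| p | g = 5 | g = 10 | g = 20 |
|---|---|---|---|
| 10% | 0.5 | 1.0 | 2.0 |
| 20% | 1.0 | 2.0 | 4.0 |
| 30% | 1.5 | 3.0 | 6.0 |
| 40% | 2.0 | 4.0 | 8.0 |

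A shift of 5 points, the smallest change that 9.3.1 treats as clinically important, needs g = 5/0.20 = 25 points at 20% missing, or 5/0.30 = 16.7 points at 30%.

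**The case against.** **The checklist is secondary.** It describes itself as a supporting document, and sensitivity analyses are often left to an SAP, which is not at hand. The second half stands as a limit on what can be said: absence from this protocol does not show that no such analysis is planned. It does not rescue item 10.8, which cites section 9.7 of this protocol.

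**Other KCCQ analyses are planned.** A reader might infer that the primary result rests on one untested observed-case summary. The protocol does not support that. It plans subgroups by time on tafamidis before entry and by supply delay, paired tests and, if feasible, a mixed model, and 9.7.4 says missing data will be reported. What remains is narrower: all of these use observed scores only, and none asks how the result would change if patients who left did worse than those who stayed.

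**Selection is not wholly ignored.** Section 9.9 has the language remark, and 9.2 allows recruitment from institutions other than the study sites. A reader might also take items 7.2 and 12.1.1 as a flat contradiction. They ask different questions, whether selection bias is addressed and whether its impact is discussed, so they are in tension and no more.

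**The size can be overstated.** Quoting only 4-6 points would rest on the largest threshold. At 5 or 10 points the shift is 1-3 points, below the protocol's threshold. The formula concerns means while the plan reports medians, and a patient who has died has no KCCQ change to shift. These points stand, so the figures serve as illustration only.

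**Conclusion.** The point holds as a mismatch with a practical consequence. Items 10.8, 12.1.1 and 12.1.3 claim content that 9.7 and 9.9 lack, and item 7.2 does not fit with 12.1.1. The consequence comes from the design and the 9.7.4 rule, not from the wrong ticks: the month-24 KCCQ summary reflects patients who lived to enrol and then stayed under observation, and nothing in this protocol tests how much that matters.

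Its size is unknown. With 20-30% missing, the shift in a mean runs from 1 to 6 points across the protocol's own three thresholds. It reaches 5 points only if the unobserved patients fare about 17 to 25 points worse. That range is wide enough to warrant one check, but it does not show that the result will be misleading.

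**What to change.** - **9.7.4 and 9.7.5:** keep observed cases as the main summary. Amend 9.7.4 to permit one sensitivity analysis, since its ban on replacing missing values would otherwise conflict with it. Describe the analysis in 9.7.5: KCCQ change by visit, with the unobserved values of patients who left alive set 5, 10 and 20 points below those of observed patients at the same visit. Show means beside the planned medians. Report deaths separately at each visit, without assigning them a score. The split uses the reason follow-up ended.
- **9.9:** add one bullet on selection (survival to enrolment, consent) and one on the lack of a comparator and hence residual confounding.
- **Annex 2:** bring items 7.2, 10.8 and 12.1 into line with the amended text.

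An analysis restricted to patients with a first KCCQ within 6 months of first dose is optional. Section 9.7.3.2 already stratifies by time on tafamidis before entry, and the restriction would keep few patients. If prescribing was even, supply immediate and enrolment on day one, about 3.5 of 13 months qualify, or 50 × 3.5/13 ≈ 13 patients.

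Cost: protocol wording and one extra table from data already planned. The reported result may look less favourable.
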